## LIST OF ABBREVIATIONS

CS	Caesarean section
CPCSP	Chronic Postsurgical Caesarean Section Pain
CPSP	Chronic Postsurgical Pain
CSEA	Combined Spinal-Epidural Anaesthesia
DSMB	Data Safety Monitoring Board
eCRF	Electronic Case Report Form
EPCS	Elective Primary Caesarean Section
ERCS	Elective Repeat Caesarean Section
GCP	Good Clinical Practice
ICF	Informed Consent Form
IEC	Independent Ethics Committee
IRB	Institutional Review Board
LSCS	Lower segment Caesarean section
PI	Principle Investigator
SAP	Statistical Analysis Plan
VAS	Visual Analogue Scale

## 1 BACKGROUND

Caesarean sections (CS) are the most commonly performed surgical procedure worldwide, with approximately one-third of all births occurring via Caesarean section in developed nations,(1-3) and over of 40% of deliveries in some nation such as Brazil(4). Specifically in the United States of America, this equates to nearly 1.3 million deliveries in 2016(4, 5). Given the difficulties associated with women undergoing a CS, coupled with expectation of recovering from a large surgical procedure whilst caring for a newborn present new challenges to the mother and her family.

Opioid analgesia is a common staple for post-surgical analgesia to aid in recovery. Unfortunately, due to the increase in Caesarean Section rates(1-3), there is more reliance on opioids to manage pain(6-9). This unfortunately is wrought with difficulties given the side-effect profile of opioid analgesics as well as their addictive potential(7). As a result, the reliance on alternative measures including surgical technique to minimise opioid requirements is an area of clinical research which requires further development(6, 9).

Anaesthetic technique and post-operative pain management play an integral role in postoperative pain. Another avenue which has been explored relates specifically to surgical techniques(2, 3, 5, 10-12). Studies have evaluated the type of incision(2, 3), method of skin closure(5), and closure of the peritoneum and its impact on post-operative pain(1). Specific to closure of the rectus fascia, Kahkhaie et al. evaluated the type of suture material used during Caesarean section and found their impact on post-operative pain(10). Finally, Trimbos et al. evaluated methods of fascial closure following midline laparotomy(12). Whilst these studies outline multiple surgical techniques and have shown impact on the risk of developing CPSP, no studies were found which directly compared the technique by which the fascia is reapproximated at the time of CS via a Pfannenstiel incision.

The purpose of this protocol is to outline our study evaluating three methods of closure of the rectus fascia and their effect on post-operative pain in patients undergoing lower segment Caesarean sections (LSCS) via a Pfannenstiel incision in a Canadian tertiary care obstetrical unit.

## 2 STUDY RATIONALE

LSCS are the most commonly performed surgical procedures worldwide. Given that much of the development of surgical approaches for trainees is based on the centre at which they are trained, there is no standardised approach which offers superiority as it relates to specific steps in the procedure. Given these issues, the notion of an evidence-based approach to fascial closure which minimises post-operative pain would be superior as it relates to the patient's return to normal activities, duration of analgesia use and overall quality of life. It is for this reason we aim to undertake this study comparing three methods of rectus fascia closure during LSCS at our unit to ascertain if there is an impact on patient's post-operative pain.

### 2.1 Hypothesis

Our study hypothesises that the presence of a thicker knot in the subcutaneous layer when closing the rectus fascia leads to more irritation of the cutaneous nerves causing more sensitivity and perceived pain by the patient. In addition, we also hypothesise that by burying the knot under the rectus fascia at the angle of the rectus incisions will further diminish the level of nerve irritation in the subcutaneous layer and will allow for a further reduction in perceived pain and analgesia requirements.

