	2. Two sutures, knots above rectus fascia									
	3. Two sutures, buried knots below rectus fascia									
DURATION OF SUBJECT	Subjects will be enrolled in the study for 10 weeks.									
PARTICIPATION AND	Screening: 1 day									
DURATION OF STUDY	Treatment: 1-2 days (subjects will be admitted to hospital)									
	Follow-up: 10 weeks									
	The total duration of subject recruitment time is 6 months, with									
	subsequent follow-up over a 10-week period after initial									
	recruitment.									
EFFICACY										
EVALUATIONS										
PRIMARY ENDPOINT	1. Analgesia use in first 72-hour period post-operatively.									
	2. Pain score questionnaire results over 10-week post-operative									
	period.									
STATISTICS										
Primary Analysis Plan	Statistical analysis will be undertaken using IMB ® SPSS ® Statistical									
	Software ver. 26 to undertake a two-sided T-test comparing group									
	1 vs. 2 and group 1 vs. 3 to assess for statistical significance in									
	analgesia use and pain scores.									
Rationale for Number	Based on a power of 80% at an alpha of 0.05, we estimate a 15%									
of Subjects	reduction in pain scores. As a result, we require a total of 255									
	subjects in this study. Given an estimated drop-out rate of 35%, we									
	aim to recruit a total of 350 participants.									
	In addition, sub-group analysis will be undertaken comparing pain									
	scores between primary and repeat Caesarean sections. Based on									
	the same power of 80% at an alpha of 0.05, with an estimation of a									
	15% difference in pain scores, we require a total of 140 subjects for									
	this sub-group analysis.									
L										

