## 6 **PROPOSED INTERVENTION**

All participants will undergo a lower segment Caesarean section via a Pfannenstiel incision. All participants involved in this study will undergo some form of regional anaesthesia (epidural, spinal, or combined spinal and epidural anaesthesia). Participants requiring general anaesthesia will be excluded from this study. Subsequently, the procedure is carried out and the delivery of

the foetus is undertaken. The hysterotomy is closed and haemostasis is then ensured in the intraabdominal cavity. At our unit, the peritoneum is not re-approximated.

Our proposed intervention involves three separate methods of closure of the rectus fascia which will be directly compared. Please refer to **Appendix A** to view diagrams outlining each method of fascial closure:

- 1) The first method of fascial closure involves the use of one #1 Polysorb™ Polyglactin 910 braided absorbable suture (Covidien™). At one angle of the rectus fascia, both the anterior and posterior leafs are grasped using Bonney forceps and the suture is tied behind this angle. This suture is then used to re-approximate the fascia in a continuous fashion across the incision. Prior to completing the suturing of this layer, the contralateral side is grasped with a Kocher clamp to bring the fascia forward so that the suture can be tied to itself behind the contralateral incision.
- 2) Method two involves two separate #1 Polysorb™ braided absorbable sutures (Covidien™). Both leafs of the rectus fascia are grasped using the Bonney forceps and the suture is placed behind the angle of the incision above the rectus fascia. Subsequent to this, the rectus fascia is reapproximated in a continuous fashion until the suture reaches the contralateral rectus abdominus muscle. Subsequently, a second #1 Polysorb™ suture is tied behind the contralateral angle in the same fashion and the remainder of the rectus fascia is reapproximated in a continuous fashion until both sutures are met, whereupon they are tied together.

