- 3) The final method again involves two separate #1 Polysorb™ absorbable sutures (Covidien™). Both leafs of the rectus fascia are grasped with the Bonney forceps and the suture is placed behind the angle of the incision ensuring that the entire knot of the suture is below the rectus fascia. Subsequent to this, the suture is run in a continuous fashion to reapproximate the fascia until reaching the contralateral rectus abdominus muscle. Subsequently, a second #1 Polysorb™ suture is tied behind the contralateral angle in the same fashion and the remainder of the rectus fascia is reapproximated in a continuous fashion until both sutures are met, whereupon they are tied together.

The remainder of the procedure is completed whereupon the subcutaneous layer is inspected for haemostasis which is achieved using the electrocautery and is reapproximated if >2cm thickness with an absorbable suture. Subsequent to this, the skin is reapproximated using a 3-0 Caprosyn® (polyglytone\*6211) suture (CovidienTM) in a subcuticular fashion.

As a means of enhancing analgesia, our centre utilises epidural morphine standard as part of their regional anaesthesia for Caesarean Sections, this utilises a single-dose of 0.15mg morphine for spinal regional anaesthesia or a single-dose of 3mg morphine for epidural regional anaesthesia. Upon completion of the procedure, the patient receives one dose of diclofenac 100mg perrectum and is initiated on oral analgesia as regional anaesthesia wears off. The patient receives a standard analgesia regimen including Tylenol 1g orally every 6 hours, Naproxen 500mg orally every 12 hours, and hydromorphone 1-2mg orally every 4 hours as required for breakthrough

pain. They are subsequently discharged home with a prescription of these three medications for a short course.

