#### **10.2 Statistical Analysis**

For our primary outcome measure, we aim to perform statistical analysis using IBM® SPSS® Version. 26 Statistics Software for Windows to perform a two-sided T-test whereby comparing groups directly. Based upon an 80% power at an alpha of 0.05, we anticipate a 15% when comparing group 1 vs 2 and group 1 vs 3, we require a sample size of 255 participants across all three groups.

Specific to our subgroup analysis evaluating primary vs. repeat caesarean section, based upon an 80% power at an alpha of 0.05, we anticipate a 15% difference in comparing these two groups using a two-sided T-test. As a result, we require a sample size of 140 participants across these two groups.

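### The hypothesis that burying the knot gives a further reduction in pain (arm 3 against arm 2) has no named comparison

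*Combined protocol and SAP*

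**What the plan says.** Section 2.1 states two hypotheses. The first is that a thicker knot in the subcutaneous layer causes more pain. The second is that burying the knot "will further diminish the level of nerve irritation in the subcutaneous layer and will allow for a further reduction in perceived pain", and reduces analgesia requirements too. No arm numbers are given.

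The synopsis lists arm 2 as "Two sutures, knots above rectus fascia" and arm 3 as "Two sutures, buried knots below rectus fascia". In section 6, method 2 has it that "the suture is placed behind the angle of the incision above the rectus fascia"; method 3 differs by "ensuring that the entire knot of the suture is below the rectus fascia". Both methods otherwise use two sutures run from opposite angles and tied where they meet.

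Pairs are named in two places. The synopsis (Primary Analysis Plan) specifies t-tests of group "1 vs. 2 and group 1 vs. 3 to assess for statistical significance in" analgesia use and pain scores. Section 10.2 gives the anticipated 15% and the sample size "when comparing group 1 vs 2 and group 1 vs 3". Elsewhere the wording is general: section 6 speaks of "three separate methods of closure of the rectus fascia which will be directly compared", the synopsis objective refers to pain scores across the three groups, and section 10.2 refers to comparing groups. Section 10 promises a detailed SAP before the final analysis.

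**The concern.** The word *further* makes the second hypothesis an increment over the two-suture closure with knots above the fascia. Only 3 vs 2 isolates that increment, and it is the one pair out of three that the plan does not name. The 1 vs 3 comparison changes two things at once, the number of sutures and the position of the knots.

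If the synopsis is followed as written, any statement about burying would have to be inferred from 1 vs 3 being significant while 1 vs 2 is not. That pattern is not a test of 3 vs 2. The named pairs do serve the general objective in section 3.1; the mismatch is with the second hypothesis.

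**Working it through.** **Which contrast the hypothesis needs.** Write m1, m2, m3 for the arm means. The strict reading is m2 − m3. A looser reading is that arm 3 improves on arm 1 by more than arm 2 does. It gives the same contrast: (m1 − m3) − (m1 − m2) = m2 − m3.

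**Effect size implied by the plan.** Section 5.2 gives 85 per arm, two-sided alpha 0.05 and 80% power. No mean or SD is given, so 85 cannot be derived from the stated 15%. Back-solving by the normal approximation gives d = (1.960 + 0.842) × √(2/85) = 0.430; the exact t-test gives d = 0.432. A 15% reduction then requires SD/mean of about 0.15/0.43 = 0.35. I take d = 0.432 as an assumption and show 0.2, 0.3 and 0.6 beside it.

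**What the two named tests show under different truths.** Simulation with normal data, equal SD, 85 per arm, unadjusted two-sided t-tests and 200,000 runs per setting:

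| Truth (means of arms 1, 2, 3) | Result | d = 0.2 | 0.3 | 0.432 | 0.6 |
|---|---|---|---|---|---|
| Burying adds nothing (0, −d, −d) | both significant | 12% | 33% | 69% | 95% |
| | 1 vs 3 only | 13% | 17% | 11% | 2% |
| Burying adds a second full effect (0, −d, −2d) | both significant | 23% | 49% | 80% | 97% |
| Burying does everything (0, 0, −d) | both significant | 1.9% | 2.5% | 3.3% | 4.5% |
| | 1 vs 3 only | 23% | 47% | 77% | 93% |
| Arm 2 halfway (0, −d/2, −d) | 1 vs 3 only | 20% | 36% | 53% | 48% |

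At d = 0.432, when arm 2 already has the full effect, both tests are significant in 69% of trials if burying adds nothing and in 80% if it adds a second full effect. These are hard to tell apart.

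**Whether the pattern can stand in for the test.** At d = 0.432, among trials showing 1 vs 3 only, a direct 3 vs 2 test is significant in 14% (burying adds nothing), 46% (arm 2 halfway) or 87% (burying does everything). It cannot.

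**Power of a direct 3 vs 2 test, unadjusted, 85 per arm (exact t-test):**

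| Effect of burying | d = 0.2 | 0.3 | 0.432 | 0.6 |
|---|---|---|---|---|
| d | 25% | 49% | 80% | 97% |
| 0.85d | 20% | 38% | 66% | 91% |
| 0.5d | 10% | 16% | 29% | 49% |

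The 80% at d = 0.432 holds by construction; no document sizes this increment. With 350 recruited and 35% lost, 350 × 0.65 / 3 ≈ 76 per arm remain. Power at d = 0.432 is then 75%, 61% and 26% for the three rows.

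**Precision.** The 95% CI half-width is t × √(2/n): 0.30 SD at 85 per arm and 0.32 SD at 76.

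**The case against.** The strongest reply is that the plan does not exclude 3 vs 2. The analysis sentence in section 10.2 is unrestricted, and the pairs come in the next sentence, which concerns sample size. Only the synopsis ties the pairs to the tests themselves. This is right as far as it goes: 3 vs 2 is neither named nor powered, but it is not ruled out. Still, wherever the plan becomes specific it names the same two pairs, and general wording commits to nothing. The promised SAP is the place for the repair, not evidence that it has been made.

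Second, the difference between arms 3 and 2 can be obtained by subtracting the two named differences, with a CI from the arm summaries. True, but that is not a planned comparison with a place in the error control.

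Third, the hypothesis is stated in advance, so even a late 3 vs 2 test would address a pre-stated question. That stands in part. The question would be pre-stated, but the test, and how alpha is shared, would be chosen after unblinding.

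Fourth, the 69% against 80% is one selected truth and one summary. With a second full effect, power for 1 vs 3 rises from 80% to over 99%, so its estimate shifts clearly. When burying does everything, the named tests also separate better. This tempers the size of the problem, but neither named test becomes a test of burying.

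Finally, section 2.1 could be reworded to match the named pairs. That would be consistent, but it drops the question that arm 3 is there to answer.

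**Conclusion.** The concern holds. It is one of consistency: section 2.1 states a hypothesis whose only direct contrast is 3 vs 2, and both places that name pairs omit it. That conclusion does not depend on any assumed effect size. It rests on mapping the hypothesis to arms through the arm definitions, since section 2.1 gives no arm numbers.

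The percentages do depend on assumptions: a d back-solved from the sample size, normal data, equal SDs and unadjusted tests. They vary widely over d from 0.2 to 0.6.

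The gap is not fatal and can be closed before unblinding. Section 7.2 keeps the blind until after database lock, so an addition made before then would count as pre-specified.

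**What to change.** In the synopsis and section 10.2, or in the SAP before unblinding, keep the two named pairs and add the third. Suggested text:

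*For each primary endpoint, groups 1 vs 2, 1 vs 3 and 3 vs 2 will be compared. Group 3 vs group 2 is the test of the second hypothesis in section 2.1. All three differences will be reported with 95% CIs.*

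Also state:
- the effect assumed for 3 vs 2 and the resulting power;
- that a non-significant 3 vs 2 would not show that burying has no effect, given the CI width;
- how error is controlled across the three tests.

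**Cost.** Reporting the extra difference and its CI needs no new patients or data. A third unadjusted test raises family-wise error per endpoint under the global null from about 9.0% to 12.1% (simulation, 400,000 runs). Controlling it costs power. The method is the sponsor's choice; at 85 per arm and d = 0.432, starting from 80% unadjusted:
- **Holm over three pairs:** 69% for a named pair when arms 2 and 3 are equal; 66% for 1 vs 3 when arm 2 is halfway.
- **Overall F-test first:** 76% and 70% in the same two cases.
- **Fixed sequence, both named pairs first:** the first pair keeps 80%, but 3 vs 2 has 61% if burying adds a second full effect and 2% if burying does everything.
- **Fixed sequence 1 vs 3, then 3 vs 2, then 1 vs 2:** 3 vs 2 has 80% and 69% in those two cases, but 1 vs 2 has 2% if burying adds nothing.

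If a sequence is used, its order should be chosen with these figures in view. Multiplicity across the two primary endpoints and the five questionnaire times is a separate matter.

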## **3** STUDY OBJECTIVES

### 3.1 Primary Objectives

The primary objective in this study is to evaluate post-operative pain in patients undergoing elective lower segment caesarean sections via a Pfannenstiel incision. The intervention in question relates specifically to the method by which the rectus fascia is closed. Participants will fill in a pain questionnaire over a period of 10 weeks at set intervals to ascertain their level of pain on visual analogue scores and requirements for analgesia.

#### 3.2 Secondary Objectives

Our secondary objective relates specifically to whether there is a difference in pain in patients undergoing primary or repeat caesarean sections. This will also be determined using sub-group analysis of participant pain scores based upon their questionnaire responses.

## 4 STUDY DESIGN

#### 4.1 Study Overview

The proposed study will be designed as a double-blinded, randomised, single-centre, clinical trial. Participants will be randomised into one of three groups based upon which method of rectus fascial closure will be undertaken. Post-operative questionnaires will be undertaken over a 10week period at set time points to elucidate post-operative pain.

#### 4.2 Strengths and Limitations

The overall strength of this study lies in its randomisation of participants as a means of minimising bias. In addition, we aim to achieve a statistically significant result which can specifically target the efficacy of these three specific techniques in fascial closure and its impact on post-operative pain. As a result, this study will help to determine if a standardised method of fascial closure is more effective as it relates to post-operative pain when patients undergo a Pfannenstiel incision during their Caesarean section.

With respect to limitations, this study only considers the use of a Polysorb™ absorbable sutures (Covidien™) as the suture of choice in closure of the rectus fascia given this is the primary suture which is used in our unit. It does not consider the use of other suture materials including delayed absorbable monofilament sutures and their impact on post-operative pain. In addition, given the subjectivity of pain perception, we accept that this may impact our findings given participants

will have varying perceptions of their pain. We hope that by randomising our participants in each group, this will help to standardise our sample across all three groups.

## 5 SUBJECT SELECTION

#### 5.1 Study Population

Our study population includes all women undergoing elective primary or repeat lower segment Caesarean sections via a Pfannenstiel incision at Sunnybrook Health Sciences Centre in Toronto, Canada. This is a tertiary care centre with approximately 4000 deliveries annually and a Caesarean section rate of 18%. The average rate of Caesarean sections in most developed countries is approximately one-third of all deliveries.

#### 5.2 Sample Size

Our sample size is based upon a power of 80% at an alpha of 0.05 based on a two-sided t-test comparing groups. Based on these findings, our total sample size in each arm is 85 participants. In total, as there are three arms, our total sample size requires 255 participants, whereby randomising 85 participants to each group. In addition, we aim to undertake a sub-group analysis comparing primary to repeat Caesarean section with a power of 80% at an alpha of 0.05. Once again, a two-sided t-test would be used and based on these findings, we would require a total sample size of 140 participants, whereby comparing 70 participants per group. Given these minimum requirements and we estimate a drop-out rate of approximately 35%, we aim to recruit a total of 350 participants to this study.

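### One stated set of inputs (two-sided t-test, alpha 0.05, 80% power, 15%) is attached to both 85 per arm and 70 per group; the alpha for each primary contrast needs to be stated, and set at 0.025

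*Combined protocol and SAP*

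**What the plan says.** Section 5.2 sizes the primary comparison as follows: "Our sample size is based upon a power of 80% at an alpha of 0.05 based on a two-sided t-test comparing groups". The result is "our total sample size in each arm is 85 participants", or 255 over three arms. The same paragraph then describes a "sub-group analysis comparing primary to repeat Caesarean section with a power of 80% at an alpha of 0.05", adds "Once again, a two-sided t-test would be used", and concludes "we would require a total sample size of 140 participants, whereby comparing 70 participants per group".

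The effect size is in the synopsis and section 10.2. Section 10.2 says of the primary comparison "we anticipate a 15% when comparing group 1 vs 2 and group 1 vs 3" (the noun is missing; the synopsis calls it a reduction in pain scores). Of primary versus repeat Caesarean section it says "we anticipate a 15% difference in comparing these two groups using a two-sided T-test". The synopsis also attaches 15% to both calculations and describes the second as using the same power and alpha as the first.

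None of the three places gives a reference mean, an SD or a standardised effect. None mentions an adjustment for making two primary contrasts, or says whether 0.05 applies to each contrast or to the pair.

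**The concern.** Both calculations are two-group, two-sided t-tests on pain scores with the same stated alpha, power and percentage difference, yet one gives 85 per group and the other 70. Something that went into at least one of them has been left out or is described incompletely.

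The missing item may be the significance threshold for the primary claim. A statistician following section 10.2 would test 1 vs 2 and 1 vs 3 each at 0.05. If 85 per arm was sized for 0.025 per contrast, the analysis as written does not match the design. A contrast with a p-value between 0.025 and 0.05 would count as positive under one reading and not under the other, and the documents do not settle which applies.

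**Working it through.** **Inputs.** From the synopsis, 5.2 and 10.2: two-sided t-test, alpha 0.05, power 80%, difference 15%, two primary contrasts sharing group 1, 85 per arm, 70 per group. Not given: mean and SD. Neither 85 nor 70 can therefore be reproduced directly, and the check works back from each to the standardised difference d (difference divided by SD) that it implies.

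**Formula.** Normal approximation: n per group = 2(z_alpha + z_power)² / d². The results below use the noncentral t, which differs slightly.

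**Implied d at 80% power.**

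| n per group | two-sided alpha | implied d | SD/mean if the difference is 15% |
|---|---|---|---|
| 70 | 0.05 | 0.4769 | 0.15/0.4769 = 31.5% |
| 85 | 0.05 | 0.4322 | 0.15/0.4322 = 34.7% |
| 85 | 0.025 | 0.4765 | 0.15/0.4765 = 31.5% |

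The first and third rows agree; the first and second do not.

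**From 70 to 85 without knowing the SD.** If d is common, it cancels and n scales with (z_alpha + z_power)²:
- alpha 0.05: (1.960 + 0.842)² = 7.849
- alpha 0.025: (2.241 + 0.842)² = 9.505
- ratio 9.505/7.849 = 1.211, and 70 × 1.211 = 84.8, which rounds up to 85

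The noncentral t at d = 0.4769 gives 84.9, again 85. A Sidak split over two contrasts gives 84.6, also 85. A split over three gives 93.5, so 94, which does not fit. At alpha 0.05 the same d needs 70 per arm, or 210 in total.

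**The other reconciliation.** Keep alpha 0.05 for both and let the SD differ. The required ratio is 0.4769/0.4322 = 1.10 (check: √(85/70) = 1.10). An SD about 10% larger relative to the mean in the primary comparison gives both 85 and 70.

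**Power under each explanation.**
- d = 0.477, 85 per arm: 80.1% at alpha 0.025 and 87.1% at 0.05.
- d = 0.432, 85 per arm: 80% at alpha 0.05 and 71.1% at 0.025. Restoring 80% at 0.025 would need 103.03, so 104 per arm.
- d = 0.432, primary versus repeat at alpha 0.05: 71.9% with exactly 70 versus 70, and 86.6% if the planned 255 evaluable women split 70/185.

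**Family-wise error.** With equal arms and a shared group 1, the two test statistics have correlation 0.5. The chance that at least one exceeds 1.96 in absolute value under the null is 9.1%. Assuming independence would give 1 − 0.95² = 9.75%; the Bonferroni bound is 10%. With each contrast at 0.025, the bound is 2 × 0.025 = 5%.

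**The case against.** A reader might infer that 85 or 70 must be wrong. The documents do not support that. Fifteen per cent of an unstated mean is not a standardised effect, and the comparisons differ in kind: randomised closure methods in one, women with and without a previous Caesarean section in the other. Different SDs are plausible, and a ratio of 1.10 is enough. Both figures are also right together if 0.05 was meant for the pair of primary contrasts.

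A reader might equally take the match at 84.9 as proof of a Bonferroni split. It is not. No section mentions a split or 0.025, and Sidak also rounds to 85. This part of the objection stands, so the protocol should not be made to assert 0.025 and 0.477 SD as the basis of 85 unless the sponsor's worksheet confirms them.

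It is also fair that 72% power for the primary-versus-repeat comparison applies only to exactly 70 versus 70. Section 5.2 treats its figures as minimum requirements, and the comparison can use all evaluable women.

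Two further arguments carry less weight. The first is that family-wise error is a separate matter from the mismatch. It would arise without the mismatch, but the mismatch is what leaves the intended threshold in doubt, and one change settles it. The second is that section 10 promises a detailed SAP before the final analysis. That could fix the threshold, but it leaves the decision rule open while data accrue.

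**Conclusion.** The point holds as one of incomplete reporting that affects the primary decision rule. With a common SD, the stated inputs cannot produce both 85 and 70. An unstated alpha of 0.025 per contrast reconciles them to the integer, and an SD about 10% larger for the primary comparison also does so; the documents do not say which applies. No sample-size figure has been shown to be wrong.

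The consequence does not depend on which explanation is true. The plan as written applies unadjusted two-sided t-tests at 0.05 to two primary contrasts, with a family-wise error of about 9.1% for one outcome. This assumes equal arms, a shared group 1 and no true difference. Testing each contrast at 0.025 brings this within 5%, with 80.1% power at the effect implied by the plan's own 70 per group, or about 71% if the primary comparison was sized at 0.05.

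The synopsis also names two primary endpoints, analgesia use and pain score. That is a separate multiplicity question, which this change does not resolve.

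**What to change.** 1. In the synopsis and section 10.2, state that 1 vs 2 and 1 vs 3 are each tested at two-sided alpha 0.025.
2. Check the sample-size worksheet, and state in section 5.2 the reference mean, SD and per-contrast alpha behind 85 and behind 70.
3. Word the power statement according to what the worksheet shows:
   - Alpha 0.025 with d = 0.477: power is 80.1% at 85 per arm.
   - Alpha 0.05 with a common d = 0.432: restate power as about 71% for each primary contrast at 0.025, and about 72% for exactly 70 versus 70 women in the primary-versus-repeat comparison (higher if all evaluable women are analysed).
   - Different SDs: state both. If the primary comparison was sized at 0.05, its power at 0.025 is again about 71%.

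The cost is wording in three places and one look at the worksheet. No patients are added; the downside is at most a less favourable stated power.

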## 7 STUDY TREATMENTS

#### 7.1 Method of Assigning Subjects to Treatment Groups

Up to 350 eligible patients will be randomly assigned to one of the three intervention groups in a 1:1 ratio using an Excel-based computer-generated randomisation scheme.

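### Recruiting 350 women does not leave the required 255 after 35% drop-out, and the unit's own caseload cannot supply 350 in the stated 6 months

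*Combined protocol and SAP*

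**What the plan says.** Section 5.2 (Sample Size) sets the requirement: "Our sample size is based upon a power of 80% at an alpha of 0.05 based on a two-sided t-test comparing groups". From this, "our total sample size in each arm is 85 participants", and for three arms "our total sample size requires 255 participants, whereby randomising 85 participants to each group". It then allows for attrition: "we estimate a drop-out rate of approximately 35%, we aim to recruit a total of 350 participants". The Synopsis repeats 255, 35% and 350.

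Two other provisions fix the number. Section 7.1 reads "Up to 350 eligible patients will be randomly assigned", which makes 350 a ceiling. Section 8 states that women who withdraw are not replaced.

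On timing, the Synopsis says "The total duration of subject recruitment time is 6 months, with" 10 weeks of follow-up after that. Section 5.1 describes the single site as a centre with "approximately 4000 deliveries annually and a Caesarean section rate of 18" per cent. Sections 5.3 and 5.4 restrict entry to elective Caesareans by Pfannenstiel incision, in singleton pregnancies, under regional anaesthesia, in women without a history of chronic pain.

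**The concern.** To keep a given number of completers at drop-out rate d, the requirement is divided by (1 − d). The 350 looks as though the requirement was multiplied by (1 + d) instead, which always falls short. The gap grows with d, and 35% is a high rate. If so, the trial cannot reach its own 255 under its own assumptions, and the 80% power statement is not what the design gives.

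The recruitment period raises a second, independent doubt. The target of 350 is almost the same as the number of Caesareans of any kind that the unit performs in 6 months. If recruitment closed on the calendar, the trial would be far smaller than planned, and a null result could be misread as evidence that the three closure methods are equivalent for pain.

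**Working it through.** **Inputs from the protocol.** Required N = 255, 85 per arm, 80% power, two-sided alpha 0.05, drop-out about 35%, recruitment 350 (section 5.2 and Synopsis). Cap of 350, equal allocation (section 7.1). No replacement (section 8). About 4000 deliveries a year, 18% by Caesarean (section 5.1). Recruitment period 6 months, one site (Synopsis).

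**Reproducing the 350.**
- Dividing: 255 / (1 − 0.35) = 392.3, so 393 (131 per arm). This does not match 350.
- Multiplying: 255 × 1.35 = 344.25. Rounded up, this fits 350.

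The protocol shows no derivation, so the multiplication is an inference. Nothing below depends on it.

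**What 350 delivers.**
- Completers at 35% loss: 350 × 0.65 = 227.5, or 75.8 per arm against 85 required.
- Largest drop-out that still leaves 255: 1 − 255/350 = 27.1%.

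**Power at 75.8 per arm.** The protocol gives a 15% effect but no mean or SD, so the 85 cannot be rebuilt. I take the protocol's premise that 85 per arm gives exactly 80% and solve for the standardised difference d with the noncentral t distribution.

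| Alpha assumed for the 85 | d giving 80% at 85 per arm | Power at 75.8 per arm |
|---|---|---|
| 0.05 two-sided | 0.432 | 75.3% |
| 0.025 two-sided | 0.4765 | 74.8% |

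The result is about 75% whether or not the 85 allowed for two comparisons.

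**Caseload in the recruitment period.**
- 4000 × 0.18 = 720 Caesareans a year, so 360 in 6 months.
- 350 / 360 = 97% of all Caesareans; 393 / 360 = 109%.
- If all 360 were eligible and consented: 360 × 0.65 = 234 completers, 78 per arm, still below 255. This step needs no outside figure beyond the protocol's own.

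**Illustration with assumed rates.** The protocol gives neither the elective share nor the consent rate. Assume 30–60% of Caesareans are elective and 50–100% of those women consent.

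| | Low end | High end |
|---|---|---|
| Recruits in 6 months | 360 × 0.30 × 0.50 = 54 | 360 × 0.60 × 1.00 = 216 |
| Completers per arm | 54 × 0.65 / 3 = 11.7 | 216 × 0.65 / 3 = 46.8 |
| Power (d = 0.432, alpha 0.05) | 17% | 54% |
| Months to recruit 350 | 6 × 350 / 54 = 39 | 6 × 350 / 216 = 9.7 |

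**The case against.** The strongest reply is that 35% need not be lost from every endpoint. One of the two primary endpoints is analgesia use in the first 72 hours, and questionnaires are sent on days 1 and 2 as well as at 2, 6 and 10 weeks. A woman lost at week 6 may already have given her early data. With d = 0.432, 350 women give about 91% power with no loss and about 84% with 20% loss. This stands as a limit on scope: 75% is the figure for an endpoint that carries the full stated loss, such as week-10 pain. It does not rescue the sample-size statement, because the protocol applies one 35% rate without splitting it by endpoint, and the Synopsis ties the calculation to pain scores.

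A second reply is that the 75% is back-calculated. That is true, and it should be stated with its condition. The shortfall from 255 to about 227 carries no such condition.

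A third is that 6 months is a forecast and not a stopping rule, so the likely consequence is longer recruitment and not 12 women per arm. That is fair. The protocol does not say whether the calendar or the number ends recruitment, and the 17–54% range applies only if the calendar does. The finding that 6 months is not credible does not rest on that range.

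Finally, the inflation slip alone costs about 5 points of power, which is modest. The timetable problem is the larger of the two.

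**Conclusion.** The concern holds. Under the protocol's own 35% drop-out, 350 recruits leave about 227 women (76 per arm) and not 255. Power falls from 80% to about 75%, given that 85 per arm yields 80% and that the endpoint bears the full loss. The target matches the requirement only if drop-out is 27% or less, and a rate described as approximately 35% does not stretch that far. The cap and the no-replacement rule leave no way to recover the difference.

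The 6-month period fails on the protocol's figures alone: even enrolling every Caesarean at the unit would leave 234 completers. How much longer recruitment would take depends on elective share and consent, which are not given; under the assumed ranges it is about 10 to 39 months for 350. Both statements need correcting before the sample-size section can be relied on.

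**What to change.** In the Synopsis and section 5.2, make the three numbers agree in one of these ways:

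- Keep 350 and restate the result: about 227 evaluable women (76 per arm) at 35% drop-out, with about 75% power if 85 per arm gives 80%.
- Raise the target to 393 (131 per arm) and change the cap in section 7.1 to match.
- Keep 350 and 255, and justify a drop-out of 27% or less.

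Replace the 6-month period with one calculated from the unit's annual number of eligible elective cases and the expected consent rate. State that recruitment ends when the target number is reached, not on a date.

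The first option is a text amendment and needs no extra patients; the stated power becomes slightly less favourable. The second adds 43 women (393 − 350). Under any option, the stated recruitment period becomes longer.
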